#### 3.3 Secondary Study Endpoints

Various secondary endpoints that will be evaluated for the study are detailed in Section 2.2.

#### 3.4 Safety Endpoints

Adverse events related to the use of the  $\mu$ Cor system and all serious adverse events will be used to assess safety during the study.

#### 4 Study Subject

#### 4.1 Inclusion Criteria

The following criteria will be used to include subjects in **phase I** portion of the study:

- 4.1.1 Healthy male and female volunteers.
- 4.1.2 Subjects older than 21 years of age.
- 4.1.3 Subjects willing to wear the  $\mu$ Cor device for up to 30 days.
- 4.1.4 Subjects willing to answer weekly phone calls from the study staff.

The following criteria will be used to include subjects in **phase II** portion of the study:

- 4.1.5 Patients with a clinical indication for outpatient cardiac monitoring.
- 4.1.6 Patients older than 21 years of age.
- 4.1.7 Patients willing to wear the  $\mu$ Cor device for up to 90 days.
- 4.1.8 Patients willing to make monthly (30-, 60-, and 90-day) office visits during the study period.
- 4.1.9 Patients willing to answer weekly phone calls regarding their health status.

#### 4.2 Exclusion Criteria

The following criteria will be used to exclude subjects from **phases I** and **II** portions of the study:

- 4.2.1 Subjects reporting or planning to be pregnant.
- 4.2.2 Subjects with any cardiac implantable electronic devices, including loop recorders.
- 4.2.3 Subjects with a wearable cardioverter defibrillator.
- 4.2.4 Subjects with Holter monitors, wearable event recorders, and other mobile cardiac telemetry devices.
- 4.2.5 Subjects with any skin condition that would prevent them from wearing the  $\mu$ Cor system.
- 4.2.6 Subjects who are non-ambulatory.
- 4.2.7 Subjects without adequate cellular transmission access that would prevent data download from the μCor device.
- 4.2.8 Subjects participating in another clinical study.

ZOLL Document Number: 90D0167 PATCH Feasibility Study

Version: C

- 4.2.9 Subjects unable to give informed consent.
- 4.2.10 Employees of ZOLL or their family members.
- 4.2.11 Subjects traveling during the study participation period that prevents planned office visits and weekly phone calls from the study coordinator.
- 4.2.12 Subjects expected to undergo a planned MRI exam during the participation period.

#### 5 Study Enrollment Plan

#### 5.1 Enrollment Strategy

Physicians with clinical research capabilities and willing to use the  $\mu$ Cor system will be identified as potential investigators for the study. Study related educational training may be provided to study coordinators and clinicians to increase awareness about the trial. In addition, study brochure describing the potential benefits and risks of the study may be provided to likely candidates for the study.

#### 5.2 Study Size

The study will enroll a maximum of 50 subjects. Six healthy volunteers will be enrolled for phase I of the study. Remaining 44 subjects will be enrolled for phase II and will have an indication of outpatient monitoring. Subjects will be enrolled from a maximum of 8 sites. All sites will be located in Europe.

#### 5.3 Enrollment Period

The anticipated total enrollment period will be 5 months. All subjects are anticipated to complete the  $\mu$ Cor wear period at 8 months from start of the study.

#### 5.4 Early Withdrawal of Subjects

#### 5.4.1 When and How to Withdraw Subjects

Subjects may voluntarily withdraw participation at point during the study period. In addition, subjects will be withdrawn from the study prior to study completion under following scenarios:

- 5.4.1.1 Skin irritation and/or rash due to use of the  $\mu$ Cor device that prevents subjects from wearing the device for longer than 72 hours.
- 5.4.1.2 Any life-threatening condition that prevents subjects from participating in the study for longer than 7 days.
- 5.4.1.3 Subjects no longer meeting the inclusion/exclusion criteria.

#### 5.4.2 Data Collection and Follow-up for Withdrawn Subjects

All data from withdrawn subjects will be retained. Reasonable attempts should be made to obtain the end of study follow-up data. At minimum, the end of study follow-up data should include survival data.

#### 6 Study Procedures

#### 6.1 Subject Recruitment and Screening

#### 6.1.1 Subject recruitment

Subjects will be identified from investigator sites. The investigator or the designated study coordinator will approach potential subjects to discuss the details of the clinical study, including benefits and risks of participating in the study.

#### 6.1.2 Subject screening

Screening of subjects will be take place based on the inclusion/exclusion criteria. For phase I of the study, healthy volunteers will be screened. For phase II, only subjects with a documented clinical indication for outpatient cardiac monitoring will be screened for the study.

#### 6.2 Scheduled Visits

#### 6.2.1 Visit 1: Screening and fitting of the μCor system

- 6.2.1.1 For phase I of the study, healthy volunteers will be screened. For phase II, a chart review of patients will be used to evaluate patients for enrollment. A screening log will be maintained.
- 6.2.1.2 Informed consent will be obtained on eligible patients who wish to participate in the study.
- 6.2.1.3 The initial clinical and demographic data will be recorded. This may be done by chart review.
- 6.2.1.4 Subjects will be trained on care and use of the  $\mu$ Cor system per the Instructions for Use manual.
- 6.2.1.5 Each site will sequentially assign a number to each subject as they are enrolled, starting at 001.
- 6.2.1.6 Subjects will be then fitted, per the Instructions for Use manual, with two μCor systems, one along the left midaxillary line and the other along the left midclavicular line. Subjects will wear the two devices for first seven days. After that, subjects with an odd number will be assigned to wear the device only

Page 13 of 27

ZOLL Document Number: 90D0167 PATCH Feasibility Study

Version: C

along the midaxillary line and those with an even number will wear the device only along midclavicular line.

- 6.2.1.7 A confirmation e-mail will be sent to the designated study staff within 1 hour of fitting and activating the devices that the  $\mu$ Cor system is able to transmit data to a remote server.
- 6.2.1.8 First monitoring report will be sent the physician-investigator or designated study staff within 24 hours of fitting and activating the devices.

#### 6.2.2 Visit 2: Wear period from 0 to 7 days

Subjects will wear two µCor devices for the first 7 days. All subjects will keep a diary to record their daily activities of living, their skin condition due to use of the µCor device/s, and the placement location of the device (Appendix A). For subjects participating in phase II of the study they will keep a dairy to record any symptoms related to heart rhythm abnormalities and heart failure (Appendix A). Symptoms associated with transient arrhythmias include syncope, near syncope, dizziness, palpitation, shortness of breath, chest discomfort, weakness, and diaphoresis. Symptoms of heart failure include: dyspnea, fatigue and weakness, edema, persistent coughing or wheezing, lack of appetite and nausea, confusion and impaired thinking, and increased heart rate. Arrhythmia monitoring reports will be provided to the physician when an actionable arrhythmia is detected per the notification specified by the physician-investigator. On day 7, the study coordinator will call the subjects to record any clinical actionable events and check on status of the device. During the call, subjects will be requested to send to send their dairy every week to the study coordinator. In addition, the study coordinator will remind the subjects to remove one of the devices, midaxillary or midclavicular, depending on whether the subjects are assigned an odd or even number. Subjects will also be instructed on how to send one of the study devices back to the sponsor.

#### 6.2.3 Visit 3: Wear period from 8 to 30 days

Study coordinators will make weekly phone calls to record any clinical actionable events and ask subjects to send their weekly diaries. During this phone call, study coordinators will answer any device related questions, and if possible help with troubleshooting per the  $\mu\text{Cor}$  Instruction for Use manual. All subjects will continue recording the requested information in their diary (Appendix A) and send their diaries to the study coordinator once a week. Arrhythmia monitoring reports will be provided to the physician when an actionable arrhythmia is detected per the notification specified by the physician-investigator. At day 30, all subjects will perform an office visit. During this visit, the study coordinator will collect subject diaries, answer questions related to the study and the device. In addition, subjects participating in phase I of the study will return all their study devices and study related material.

#### 6.2.4 Visit 4 and 5: Wear period from 31 to 90 days

Only subjects participating in phase II of the study will wear the device up to 90 days. All subjects will continue recording the requested information in their diary (Appendix A) and send their diaries to the study coordinator once a week. Study coordinators will make weekly phone calls to record any clinical actionable events. During this phone call, study coordinators will ask the subjects to send their diary, answer any device related questions, and if possible help with troubleshooting per the  $\mu$ Cor Instruction for Use manual. Arrhythmia monitoring reports will be provided to the physician when an actionable

arrhythmia is detected per the notification specified by the physician-investigator. At day 60 and 90, subjects will perform an office visit. During this visit, study coordinator will collect the subject diaries, and answer questions related to study and the device.

#### 6.2.5 Visit 5: End of study follow-up

End of study follow-up will take place at the 90 day office visit or when the subject decides to end the study. Study coordinators will be responsible for collecting the subject diaries, any adverse events, and the study device.

#### 6.3 Unscheduled Visits

Based on the physician-investigator discretion, subjects can be seen at any time during the study period.

#### 6.4 Long-term Clinical Outcome Assessment

NA

#### 6.5 Study Procedures Flowchart (or Table)

Summary of the activities and procedures to be followed at each visit is as detailed below (Table I)

Table I

Table I					
	Visit 1 (Day 0)	Visit 2 (Day 7)	Visit 3 (Day 30)	Visit 4 (Day 60)	Visit 5 (Day 90 / End of Study)
Eligibility	Х				
Consent	Χ				
Subject number assignment	Х				
Clinical and demographic data	Х				
Device training	Χ				
Device fitting	X				
Data transmission confirmation	Х				
Monitoring report	X				
Collection of subject diary		Х	Х	X	Х
Weekly phone calls		X	X	Χ	X
Subject diaries		X	X	Χ	X
Office visit			X	X	X
Filling of case report forms	Х	Х	X	X	X
Return of device 1		Х			
Return of device 2			X (for phase I subjects)		Х
Survival information		X	X	Χ	X

#### 6.6 Blinding and Unblinding of Study

Investigator-physicians and study staff will not be blinded to the ECG data. They will be blinded to the thoracic impedance, respiration rate, activity, and posture data. Furthermore, all patients will be blinded to all device data.

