#### 1.4 Study Device

#### 1.4.1 System Components

The µCor System consists of the following components:

- A) Patch
- B) Sensor
- C) Charger
- D) Data transmission device (Gateway)
- E) Server

Once activated, the wearable Sensor automatically acquires ECG, thoracic impedance, Heart Rate, Respiration Rate, Activity, and Posture measurements. Patients can also activate a patient trigger when they experience symptoms such as palpitations, shortness

of breath, or lightheadedness by double tapping the Sensor when it is on the body. Data are automatically transmitted from the Sensor to the Data transmission device, and from there to the Server for analysis (see Fig. 1). Certified technicians at the Monitoring Center review the data generated by the Server and prepare reports according to the pre-defined criteria as requested by the prescribing physician. Data provided in the report will aid the prescribing physicians in the diagnosis and identification of various clinical conditions, events and/or trends. The  $\mu Cor$  System is designed for use in outpatient clinic and home settings.

[figure not shown]

Figure 1: Data transmission of the μCor System

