#### 2 Study Objectives

#### 2.1 Primary Objective(s)

The primary objective of this study is to observe the feasibility of the novel  $\mu$ Cor system to remotely monitor patients. Feasibility will be assessed in terms of:

- 2.1.1 Logistics of equipping patients with the  $\mu$ Cor system in the physician's office. This will include verifying that the system is able to transmit data to a remote server and that a monitoring report is received by the physician's office.
- 2.1.2 Subject's ability to wear the device for the specified time period of up to 90 days.
- 2.1.3 Subject's ability to place the device in the correct anatomical position during every reapplication, as described in the patient instructions for use. Device placement case report forms and daily device data signal quality will be used to track the accuracy of device placement and repeatability.
- 2.1.4 Ability of the system to transmit data daily to the remote servers for processing.
- 2.1.5 Ability to provide a timely arrhythmia monitoring (daily, episodic, and end of monitoring) reports to physicians.
- 2.1.6 Documenting the following clinically actionable events in an outpatient setting via weekly phone calls to the subject:
  - 2.1.6.1 Emergency room visits
  - 2.1.6.2 Unplanned physician visits
  - 2.1.6.3 New arrhythmia and heart failure (HF) symptoms
  - 2.1.6.4 All-cause and HF hospitalizations
  - 2.1.6.5 Alterations and additions in HF and cardiac medications
  - 2.1.6.6 All-cause and cardiovascular mortality at 90 days

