#### 2.2 Secondary Objective(s)

A number of **secondary objectives** will be evaluated and these will include:

- 2.2.1 Equivalency of data recorded by the device placed along the left midaxillary line versus the data recoded by the device placed along the left midclavicular line.
- 2.2.2 Correlation between detected heart rhythm abnormalities and any clinically actionable events.
- 2.2.3 Correlation between detected thoracic fluid content changes and any clinically actionable events.

Page 7 of 27

ZOLL Document Number: 90D0167 PATCH Feasibility Study

Version: C

- 2.2.4 Correlation between changes in thoracic fluid content and/or detected heart rhythm abnormalities with all-cause and cardiovascular mortality.
- 2.2.5 Short term (days), mid-term (weeks), and long-term (months) stability of the device recorded data in the same patient.
- 2.2.6 Stability of the device recorded data with multiple reapplications of the μCor system.

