position. Subjects will use a diary to keep a daily log of their daily activities of living, any symptoms related to heart rhythm abnormalities and heart failure, their skin condition due to use of the  $\mu$ Cor device/s, and the placement location of the device/s (Appendix A). Data will be acquired with the  $\mu$ Cor system and wirelessly transmitted daily to a remote server for processing, generating thoracic fluid content, ECG, heart rate, respiration rate, activity, and posture measurements. Investigators will have access only to ECG data. Study staff will make weekly phone calls to subjects and record any new clinical actionable events. Furthermore, the study staff will ask the subject send their diaries after each week of wear to the study coordinator. Patients will have monthly office visits. At the end of the participation period (anticipated 90 days), patients will end wear and will complete the study follow-up questionnaire.

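### Staff who may see the ECG data also make the weekly calls that record events, so softer events could be captured more fully in weeks with an arrhythmia report and the association in objective 2.2.2 could be inflated

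*Combined protocol and SAP*

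**What the plan says.** Section 6.6 of the protocol sets the blinding: "Investigator-physicians and study staff will not be blinded to the ECG data". The same section hides thoracic impedance, respiration rate, activity and posture from investigators and staff, and adds that "all patients will be blinded to all device data".

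Section 3.1, on phase II, gives the recording of events to the same group: "Study staff will make weekly phone calls to subjects and record any new clinical actionable events". Sections 6.2.2 to 6.2.4 identify the caller. For the first week: "On day 7, the study coordinator will call the subjects to record any clinical actionable events and check on status of the device". In later weeks the coordinators also answer device questions and troubleshoot during the calls.

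Section 2.1.6 makes the calls the source of the events: "Documenting the following clinically actionable events in an outpatient setting via weekly phone calls to the subject". Its list runs from deaths, hospitalizations and emergency room visits to unplanned physician visits, medication changes and "New arrhythmia and heart failure (HF) symptoms".

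Objective 2.2.2 is "Correlation between detected heart rhythm abnormalities and any clinically actionable events". Section 8.4 provides descriptive statistics and qualitative analysis only, and section 8.3 sets no acceptance criteria.

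On reports, section 6.2.1.8 sends the first one to the physician-investigator or designated study staff. Sections 6.2.2 to 6.2.4 send later arrhythmia reports to the physician.

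**The concern.** In 2.2.2 the exposure is a detected arrhythmia and the outcome is an event recorded by telephone. The group allowed to see the exposure also elicits the outcome. A caller who knows that a report came in that week may probe symptoms more closely, or note a marginal contact that would otherwise go unrecorded. This recording bias is separate from any real care that a report sets in motion.

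The protocol already protects the parallel objective. Because thoracic impedance is hidden from staff, 2.2.3 (fluid changes against the same events) is not open to this bias; 2.2.2 is.

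At stake is the reading of 2.2.2 as evidence that device-detected rhythm findings track clinical events. If nobody notes whether a report had been seen before a call, the analyst cannot later separate the calls made with that knowledge from the others.

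**Working it through.** The plan gives no expected correlation, event rate or sample size calculation (section 8.1), so there is no figure to reproduce. The check has two parts.

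**1. Does the text create the path?**

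- Exposure visible to staff: yes for ECG, no for thoracic impedance (6.6).
- Outcome recorded by staff: yes, by weekly call (3.1, 6.2.2 to 6.2.4).
- Calls are the named source of events: yes (2.1.6).
- Those events enter the objective: yes (2.2.2).
- Countermeasure in the protocol text: none found. It describes no fixed call wording, no caller without ECG access and no event adjudication.
- A less exposed symptom source: yes. Phase II patients keep a symptom diary with time and duration (Appendix A), sent in weekly. The protocol does not say that 2.2.2 uses it.

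**2. How large could the effect be?** Every rate below is an assumption; none is in the protocol.

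- Weekly event risk p = 0.10, unrelated to rhythm.
- Share of hard events h = 0.5, always captured.
- Soft-event capture s0 = 0.50 in ordinary weeks, and s1 = 0.60, 0.70 or 0.90 in weeks with a report.

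Recorded risk = p × [h + (1 − h) × s]. Apparent odds ratio = [p1/(1 − p1)] / [p0/(1 − p0)].

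Ordinary weeks: p0 = 0.10 × (0.5 + 0.5 × 0.50) = 0.075, odds 0.0811.

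| s1 | Recorded risk p1 | Odds | Apparent odds ratio |
|---|---|---|---|
| 0.60 | 0.080 | 0.0870 | 1.07 |
| 0.70 | 0.085 | 0.0929 | 1.15 |
| 0.90 | 0.095 | 0.1050 | 1.29 |

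If s1 = s0, the odds ratio is 1.00.

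For the soft events alone (risk 0.05), recorded risk is 0.025 against 0.030, 0.035 or 0.045, and the odds ratios are 1.21, 1.41 and 1.84. The hard events dilute the bias in a pooled analysis, so it would show most in the symptom component.

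**Sensitivity to the capture rates.** With capture of 90% in report weeks against 80%, 70% or 60% in other weeks, and half the events hard, the risk ratio is (0.5 + 0.5 × 0.9)/(0.5 + 0.5 × s0) = 0.95/0.90, 0.95/0.85 or 0.95/0.80, that is 1.06, 1.12 or 1.19.

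**Set against the precision available.** At most 44 patients × 90/7 weeks = 566 patient-weeks. If 20% of weeks have a report (assumed), that is 113 against 453 weeks. At recorded risks of 0.085 and 0.075, about 9.6 and 33.9 weeks have an event. SE(log OR) = √(1/9.6 + 1/103.5 + 1/33.9 + 1/418.6) = 0.38, so a 95% interval around 1.15 runs from about 0.54 to 2.42. This treats weeks as independent, which flatters the precision.

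**The case against.** The strongest reply is that the documents show an opportunity for bias, not its occurrence. A reader might infer that the coordinator reads each arrhythmia report before calling, questions harder in those weeks, and that 2.2.2 would therefore show an association even if none existed. The text does not support that. Section 6.6 permits staff to see ECG data, but later reports are addressed to the physician, and nothing describes how callers question patients. This part of the objection stands: the bias is possible, not documented.

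Second, a standard call form may already exist. Section 12.3.1 places the CRFs in a separate document that was not available here. The event list in 2.1.6 is fixed and everyone is called weekly. This stands too, and it makes part of the fix a matter of citation.

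Third, a reader might apply differential capture to every event and obtain odds ratios of 1.21, 1.43 and 1.88 (recorded risk of 5% against 6%, 7% and 9%). Those figures are too large for the event list as written, because deaths and admissions hardly depend on how a caller asks.

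Fourth, 2.2.2 is secondary and descriptive, and its precision is poor: the interval above is far wider than the bias. That limits the consequence. It does not remove it, because the bias has a direction and chance error does not.

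Fifth, a report may itself prompt a visit or treatment, and both can count as events under 2.1.6. Standardizing the calls would not remove that path, and a patient contacted after a report may no longer be fully blind when completing the diary. This stands, and is why such events need separate reporting.

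Finally, the sensor's symptom trigger, activated "by double tapping the Sensor when it is on the body", might look like an ideal blinded outcome. Section 1.4.1 does not say whether a tap leads to ECG review. If it does, outcome and arrhythmia detection would be linked. Nor is the absence of the trigger from section 12.1 a specific gap, since that list names no physiological device signal at all.

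**Conclusion.** The point holds as a caution with a cheap remedy. Unblinded staff may record the events that 2.2.2 relates to ECG findings, and the protocol text contains no measure to keep capture equal across weeks. The association could be inflated, mainly through new symptoms and less through unplanned visits and medication changes.

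The illustrative size is an odds ratio of about 1.07 to 1.29 for all events together, given a 10% weekly risk, half of events hard and fully captured, and soft-event capture of 50% against 60% to 90%. The direction is upward whenever capture is better in report weeks; the size cannot be derived from the documents. The effect is on interpretation: no test or acceptance criterion depends on it.

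**What to change.** For 2.2.2, state in section 8.4 that:

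- Symptom events and their times come from the blinded patient's diary (Appendix A).
- Visits, admissions and medication changes come from the weekly call, using one fixed-wording form asked identically every week. If the CRF document already contains such a form, cite it.
- The form records whether an arrhythmia report had been seen since the last call.
- Results are shown separately for symptoms, for hard events, and for visits or medication changes that followed a report.
- Double-tap triggers are supportive data only and not the primary symptom outcome.

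The cost is a call script, one tick box and a few lines in the analysis section, with no added staff. The downside is less conversational calls and dependence on diary completion. Notification of physicians is unchanged.
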